
1. Individuals diagnosed with generalized PN, defined as the presence of ≥ 10 pruriginous nodules, involving at least 2 distinct anatomical areas: for example, either 2 limbs; or a single limb and some axial portion of the body. Individuals with only axial lesions but involving 2 distinct anatomical areas that have no peripheral nervous system overlap are also eligible: for example, lesions involving a portion of the cranium and a portion of the trunk of the body. For purposes of this study, the axial portion will be defined as any non-appendicular portion of the body.2. If there is any history of a primary pruritic skin condition other than PN, that condition must have been inactive for at least 6 months prior to screening.3. Subjects with a history of acute secondary dermatoses within the preceding 6 months may enroll only if the dermatosis has resolved completely as follows per medical history or patient self-report and current clinical assessment: (a) Localized contact dermatitis, environmental exposures, superficial burns, or viral exanthems must have been resolved for at least 4 weeks prior to screening. (b) Skin or environmental infestations, such as scabies, lice, or bed bugs, must have been resolved for at least 8 weeks prior to screening.4. Any identified systemic, non-dermatologic disease that could be a potential cause of concomitant pruritus (e.g., thyroid disease, celiac disease, hepatitis C virus [HCV]) must either have resolved, been successfully treated (i.e., HCV RNA negative), or must be successfully managed with stable, optimized treatment (e.g., thyroid replacement, dietary management with resolution of symptoms, respectively) for at least 3 months prior to screening.5. WI-NRS score, recorded daily over the 7 contiguous days prior to and including the day of the baseline visit via electronic diary, must have at least 5 measurements recorded and all individual measurements must be ≥ 6. The arithmetic mean value of the measurements must be ≥ 7 as confirmed by the Trialogics Eligibility Check report immediately prior to randomization. The last WI-NRS value used in the calculation should be recorded on the day of the baseline visit and prior to dosing.6. Subjects using antidepressants must be on a stable dose for a minimum of 4 weeks prior to screening and must be willing to remain on their stable dose for the entire duration of the study.7. Subjects who are human immunodeficiency virus (HIV) positive may enroll if they meet the following criteria: (a) currently on a stable (> 6 months stable use) and well tolerated highly active antiretroviral therapy regimen; (b) CD4 count > 500 cells/mL; and (c) HIV ribonucleic acid (RNA) < 50 copies/mL documented for at least 6 months prior to enrollment. If enrolled, these subjects should continue to have their CD4 and HIV RNA monitored by their HIV provider per their standard of care for the duration of		

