6. Subjects using antidepressants must be on a stable dose for a minimum of 4 weeks prior to screening and must be willing to remain on their stable dose for the entire duration of the study.
7. Subjects who are human immunodeficiency virus (HIV) positive may enroll if they meet the following criteria: (a) currently on a stable (> 6 months stable use) and well tolerated highly active antiretroviral therapy regimen; (b) CD4 count > 500 cells/mL; and (c) HIV ribonucleic acid (RNA) < 50 copies/mL documented for at least 6 months prior to enrollment. If enrolled, these subjects should continue to have their CD4 and HIV RNA monitored by their HIV provider per their standard of care for the duration of the TR11 study, and the data should be reported and documented at the next study visit.
8. Females of childbearing potential must be using an acceptable method of birth control (if sexually active) for 14 days prior to randomization and throughout the study. All females of childbearing potential must have a negative pregnancy test at the screening and baseline visits.

For the purpose of this study, all females are considered to be of childbearing potential unless they are postmenopausal (i.e., at least 1 year since last menses and age > 50 years) or surgically sterile (i.e., tubal ligation, hysterectomy, and/or bilateral oophorectomy).

Sexually active female subjects of childbearing potential are required to use 1 barrier method (e.g., condom, cervical cap, or diaphragm) of contraception in addition to 1 other method (e.g., intrauterine device in place at least 1-month, stable hormonal contraception for at least 3 months, or Essure procedure, or spermicide).

Female subjects who are abstinent may participate in the study; however, they must be counseled on the requirement to use appropriate contraception should they become sexually active. This counseling should occur at each study visit and must be documented in source records.

9. Age 18 years and older at the time of consent, and a life expectancy of at least 18 months.
10. Willing and able to understand and provide written informed consent.
11. Willing and able to comply with study requirements and restrictions.
12. Agree to the confidential use and storage of all data and use of all anonymized data for publication including scientific publication.

9.5.2 *Exclusion Criteria*

Subjects meeting any of the following criteria must not be enrolled in the study:

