1. Pruritus due to localized PN (only 1 body part affected, for example only 1 arm).

2. Active, uncontrolled, pruritic dermatoses in need of treatment (such as atopic dermatitis or bullous pemphigoid for example).
3. Prurigo Nodularis associated with a history of atopic dermatitis is excluded if acute eczematous lesions are present, as characterized by erythematous, active predominant lichenified plaques with oozing and crusting.
4. History of a major psychiatric disorder such as bipolar disorder or schizophrenia is excluded. Subjects with a history of isolated major depression > 3 years previously may be eligible for enrollment if they have access to appropriate psychiatric care. An 'isolated major depression' is defined as a single event of depression that includes recurrent thoughts of death, recurrent suicidal ideation with or without a specific plan, or any history of a suicide attempt. Enrollment must be approved by the Medical Monitor. Subjects with general depression who are considered stable may be enrolled.
5. Serum bilirubin > 1.5 × upper limit of normal range at screening unless explained by a clinical diagnosis of Gilbert's Syndrome.
6. Serum hepatic alanine aminotransferase or aspartate aminotransferase enzymes > 100 U/L at screening.
7. Estimated glomerular filtration rate ≤ 44 mL/min/1.73 m² at screening.
8. Significant medical condition, occupational restrictions (see [Section 9.3](#)), and/or other factors that in the opinion of the Investigator may interfere with the conduct of the study.
9. Subjects who have an active malignancy (either solid tumor or hematologic) are excluded. Subjects who have a past history of malignancy and who have no evidence of active disease but who continue on therapy to prevent disease recurrence (i.e., tamoxifen for breast cancer, testosterone blockade for prostate cancer, etc.), may be eligible if approved by the Medical Monitor.
10. History of active substance abuse within the past 3 years.
11. Known intolerance of, or hypersensitivity or allergy to nalbuphine or vehicle components.
12. Pregnant or lactating females.
13. Concurrent enrollment in an ongoing clinical trial or anticipated enrollment in a concurrent clinical trial. Potential subjects who are actively participating in the safety follow-up of an ongoing COVID-19 vaccination trial may enroll in this study if they meet the following criteria:

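### Inclusion Criterion 7(b) states the CD4 threshold per mL; read literally it excludes practically no HIV-positive candidate, so the sponsor should confirm the unit

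*Protocol*

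**What the plan says.** Inclusion Criterion 7 (Protocol Section 9.5.1) admits HIV-positive candidates who meet three conditions together:

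- (a) "currently on a stable (> 6 months stable use) and well tolerated highly active antiretroviral therapy regimen";
- (b) "CD4 count > 500 cells/mL";
- (c) "HIV ribonucleic acid (RNA) < 50 copies/mL documented for at least 6 months prior to enrollment".

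The synopsis repeats the CD4 condition in the same unit: "b) CD4 count > 500 cells/mL". The criterion adds that, once enrolled, "these subjects should continue to have their CD4 and HIV RNA monitored by their HIV provider per their standard of care", with the results reported to the study. It does not restate a CD4 unit there.

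CD4 is not among the study laboratory tests in Protocol Table-4, so that table supplies no unit either. The SAP gives no CD4 value.

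**The concern.** A CD4 cut-off of 500 is recognisable as a number, but the unit attached to it is unexpected. If CD4 is reported per microlitre, a limit expressed per mL is three orders of magnitude lower than the same number in the reporting unit, and the condition stops working as a filter. The two statements agree with each other, so a site that doubts the unit finds no second version in the protocol to check against.

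What is at stake is one entry condition for one subgroup. As written, a candidate with almost any measurable CD4 count satisfies (b), and enrolling that candidate on (b) would not count as an eligibility deviation. The neighbouring viral-load limit in (c) is also per mL, and its unit is not questioned here. The mL in (b) may have been carried over from (c), but the documents do not show this.

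**Working it through.** The 500 is a stated cut-off with no derivation in the protocol or SAP, so there is no planned figure to reproduce. The check is a unit conversion.

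**Inputs**

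- Threshold: more than 500 cells/mL (synopsis and Section 9.5.1, Criterion 7(b)).
- Conversion: 1 mL = 1000 microlitres.
- Assumption: CD4 counts are reported in cells per microlitre (the same as cells/mm³). This is general laboratory convention and is not stated in the documents.

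**Conversion**

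- Literal threshold: 500 cells/mL ÷ 1000 = 0.5 cells per microlitre.
- The same number per microlitre: 500 × 1000 = 500,000 cells/mL.
- Ratio: 500,000 ÷ 500 = 1000.

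**Who passes condition (b)**

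| Count per microlitre | Count per mL | Passes > 500 per mL (as written) | Passes > 500 per microlitre |
|---|---|---|---|
| 1 | 1,000 | yes | no |
| 50 | 50,000 | yes | no |
| 200 | 200,000 | yes | no |
| 350 | 350,000 | yes | no |
| 500 | 500,000 | yes | no |
| 501 | 501,000 | yes | yes |

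A count of 20 per microlitre is 20,000 per mL, which clears the written limit by a factor of 20,000 ÷ 500 = 40. Every count above 0.5 and up to 500 per microlitre passes (b) as written but would fail the same number per microlitre. The second reading shows the size of the discrepancy; it is not offered as the correct threshold.

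**What remains in force if (b) is empty**

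- 7(a): more than 6 months on a stable, tolerated antiretroviral regimen.
- 7(c): HIV RNA below 50 copies/mL, documented for at least 6 months.
- Exclusion Criterion 8, which begins "Significant medical condition, occupational restrictions" and leaves the decision to the investigator's opinion.
- Follow-up of CD4 and HIV RNA by the HIV provider. This applies after enrolment, so it is not an entry filter.

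**Effect on the analysis**

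The sample-size, power and alpha statements do not depend on Criterion 7. The primary analysis uses the modified intent-to-treat population (randomised and dosed), which does not depend on it either. The per-protocol examples in SAP Section 6.3 name inclusion criteria 1 to 6, so Criterion 7 is not listed there.

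**The case against.** The strongest reply is that this is a slip in a unit label. Site staff would probably apply 500 to whatever unit the laboratory report shows, and nothing in the documents suggests that anyone would multiply a routine result by 1000 to admit a patient. That is plausible and bears on severity. It does not make the text right, and the eligibility checklist and eCRF that would show what sites applied are not part of the public documents.

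A reader might infer that the immune-status safeguard for HIV-positive subjects is gone. That goes too far. One of three joint conditions is emptied, and the others still apply together with Exclusion Criterion 8. It is fair to say that (b) is the only fixed CD4 condition at entry. However, no passage ties that cut-off to a risk of the study drug: the risk/benefit discussion in Section 9.4 covers dependence, endocrine effects, serotonin syndrome and respiratory depression, and names no immune or infection risk.

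A reader might also infer that sites reached opposite decisions on similar patients. No passage supports this, and the number of HIV-positive subjects is not given.

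A lost character is a further possibility, with a μ rendered as m in the electronic text. It is unlikely, because the μ sign appears correctly in Section 7.2 and in Table-3.

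Finally, the remaining enrolment period may be short. Version 7 is dated 21 July 2021 and the Week 14 endpoint was planned for December 2021. Week 14 falls on Day 98, so randomisation would have to end by about late September 2021. This limits the practical value of an amendment, but not the case for settling which unit was meant.

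**Conclusion.** The point holds as a minor correction to an entry threshold. Condition 7(b) as written equals 0.5 cells per microlitre, 1000-fold below the same number per microlitre, and screens out practically no HIV-positive candidate with a measurable count. The 1000-fold factor is exact. That it represents an error rests on the assumption that CD4 is reported, and was meant, per microlitre. The documents do not contradict that assumption but do not confirm it.

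The effect is confined to the CD4 part of Criterion 7 and to HIV-positive candidates. No efficacy or safety conclusion of the trial is put in doubt by it.

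**What to change.** The sponsor should confirm the intended CD4 unit and, where it differs from the text, correct Criterion 7(b) in both the synopsis and Section 9.5.1, by administrative memo or in the next amendment. The eligibility checklist and eCRF should be checked for the same unit. The choice of threshold stays with the sponsor.

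The cost is two small text edits and one check of the forms, with no change to sample size, procedures or analysis. There is precedent for the route: the amendment history shows that an inequality sign in Inclusion Criterion 5 was handled by administrative clarification and amendment, and that a TSH unit was changed in Amendment 2.

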9.6 Premature Discontinuation of Investigational Product Treatment

Subjects who complete investigational product treatment through the full study treatment course are considered to have completed treatment with the investigational product (even if some doses have been missed). Subjects who discontinue investigational product, prior to 52 weeks of treatment will be considered to have prematurely discontinued and will be asked to complete the following visits (unless consent is withdrawn):

- If the decision to discontinue treatment is made during an onsite study visit (scheduled or unscheduled), perform the procedures and assessments outlined in the Off-Treatment visit, regardless of where they are in the study visit schedule.
- If the decision to discontinue treatment is made while the subject is not at a study visit, schedulea visit as soon as logically possible, but no later than 2 weeks later, to perform the procedures and assessments described in the Off-Treatment visit. Upon notification that the subject has permanently stopped dosing, the site should immediately update the subject’s status on the Trialogics web portal, in order to launch the SOWS, and instruct the subject to begin entering their SOWS data daily via the e-diary for the next 14 days.
- Schedule the subject to return to the clinic 2 weeks after completion of the Off-Treatment visit and perform the procedures and assessments outlined in the Last Visit, regardless of where they are in the study visit schedule.

- Schedule the End of Study telephone call with the subject 4 weeks after completion of the Off- Treatment visit and perform the procedures and assessments outlined in the schedule of events for this visit, regardless of where they are in the study visit schedule.
- If discontinuation of investigational product occurs any time between Day 1 and the Week 14 visit, the subject will be asked to complete the Off-Treatment visit, the Last Visit, and the End of Study visit telephone call, and to return to the clinic for the study schedule planned Week 14 visit.

9.7 Premature Withdrawal of Subjects from the Study

All subjects who receive study treatment should remain in the study whenever possible. If possible and appropriate, subjects for whom withdrawal is considered for the reasons identified with an asterisk below should discontinue investigational product, but are asked to provide complete data as per [Section 9.6](#). Reasons for withdrawal of the subject from the study, not just discontinuation of investigational product, include:

- Withdrawal of consent for study participation
- Sponsor terminates the study for any reason
- Investigator decision *
- The Investigator may withdraw any subject from the study if, in the Investigator's opinion, it is not in the subject's best interest to continue on the study *
- Develops a QTcF > 500 ms (mean of 3 ECG QTcF values) in subjects who were randomized **without** ECG findings of RBBB and/or QRS \geq 120 ms.
- Develops QTcF > 530 ms (mean of 3 ECG QTcF values) in subjects who were randomized **with** ECG findings of RBBB and/or QRS \geq 120 ms.
- Increase from QTcF baseline of >60 ms (mean determination from 3 ECG values).
- Death of the subject

Subjects who prematurely discontinue from the study will be asked: (1) to undergo and complete procedures and evaluations that may be necessary to ensure that the subject is free of untoward effects; and (2) to seek appropriate follow-up for any continuing problems. The date on which the subject is withdrawn from the study and the reason for discontinuation will be recorded on the electronic case report form (eCRF). Subjects who withdraw from the study will not be replaced.

10 TREATMENT OF SUBJECTS

10.1 Identity of Investigational Product

The investigational product in this trial is NAL ER tablets or matching placebo tablets. The NAL ER tablets are either round, white to off-white, film-coated tablets containing either 27 or 54 mg of nalbuphine (equivalent to approximately 30 or 60 mg nalbuphine HCl); or oval, white to off-white, film-coated tablets containing 162 mg of nalbuphine (equivalent to approximately 180 mg

nalbuphine HCl). The 27 and 54 mg NAL ER round tablets are identical in appearance. Matching placebo tablets will be used for both tablet shapes (round tablets to represent the 27 and 54 mg tablets, and oval shaped tablets to represent the 162 mg tablets).

All investigational product will be supplied by the Sponsor.

10.1.1 Administration of Study Treatments

Double-blind Treatment

Following randomization, the subject will be dispensed a 2-week blister card for the double-blind titration period. Dosing will consist of 3 tablets for the AM dose and 3 tablets for the PM dose. Arm 1 will consist of a combination of 27 mg/54 mg/placebo tablets, and Arm 2 will consist of placebo tablets only. Note: Although both AM and PM doses are present on Day 1, only the PM dose will be taken (both Arms).

At the Week 2 end of titration visit, subjects in Arm 1 will be given one 70 count bottle of NAL ER 162 mg tablets and subject in Arm 2 will be given one 70 count bottle of placebo tablets. Additional bottles will be dispensed at subsequent study visits. At each visit at which investigational product is to be dispensed, enough investigational product should be supplied to ensure that a sufficient number of tablets are available for dosing until the next visit, allowing for visit windows and/or the possibility of a late visit.

Subject dosing information for the double-blind treatment will be available in the Pharmacy Manual provided to the site. Additionally, all subjects are to be provided with the “Instructions for Taking TR11 Study Medication” which outlines dosing instructions for this treatment period.

Open-label Treatment

Subjects will be dispensed a 2-week blister card for the extension titration period. Dosing will consist of 3 tablets for the AM dose (starting on Day 2) and 3 tablets for the PM dose. (Note: There will not be any tablets to take on Day 1 AM for both Arms 1 and 2). For subjects previously assigned to Arm 2 of the double-blind treatment, the titration card will consist of combinations of either 27 mg/54 mg/placebo tablets to crossover to NAL ER. To maintain the blind, subjects previously assigned to Arm 1 will be given a card containing 3 active 54 mg NAL ER tablets for the AM dose and 3 active 54 mg NAL ER tablets for the PM dose.

At the Week 16 end of titration visit, all subjects will be given 1 x 70-count bottle for the start of the open-label fixed-dose period containing 162 mg NAL ER tablets. Additional bottles will be dispensed at subsequent study visits and subjects should again be dispensed enough investigational product to ensure that a sufficient number of tablets are available for dosing until the next visit, allowing for visit windows and/or the possibility of a late visit.

Subject dosing information for the open-label treatment will be available in the Pharmacy Manual provided to the site. Additionally, all subjects are to be provided with the “Instructions for Taking TR11 Study Medication” which outlines the dosing instructions for this treatment period.

Investigational product can be taken with or without food, as whole tablets (without crushing or chewing). Subjects will be instructed to take the AM and PM investigational product tablets at the same times of the day, 12 hours apart (\pm 2 hours), preferably with 240 mL (approximately 8 ounces) of water. For example, if a subject is taking the investigational product at 9:00 AM and 9:00 PM but forgets to take the 9:00 AM dose, he may take the 9:00 AM dose as late as 11:00 AM. After that time, the subject should skip the 9:00 AM dose and, instead, take the regularly scheduled next dose at 9:00 PM.

Subjects will confirm (in the e-diary) whether or not they took their dose(s) and the dosing time for both the AM and the PM dose. Any discrepancies between the dosing records in the e-diary and the number of actual versus expected tablets (based on the e-diary reporting) returned to the site, should be documented at the actual visit in which investigational product is returned. This should occur at every visit during the investigational product drug accountability and investigational product compliance assessments.

10.1.2 Down-titration

At the regularly scheduled study visits for Week 28, Week 32, and Week 36, an elective dose reduction to a 108 mg NAL ER BID dose may be considered for subjects who achieve a confirmed WI-NRS \leq 3 **and** visible lesion healing as assessed by an improvement of at least 1 category in the PAS healing activity score, Item 5b. For example, if “0-24%” of PN lesions at baseline were assessed as ‘healed’, then a 1-category change means that “25-50%” of current Week 28 PN lesions are now evaluated as ‘healed’. The WI-NRS scores at and after Week 24 will be available to site staff via the Trialogics portal in order to assess eligibility for this down-titration. The decision to dose reduce is at the discretion of the Investigator and with the agreement of the subject, but once this dosing has started, no re-escalation is permitted. Dose reduction is not permitted prior to Study Week 28 or after Study Week 36.

